16.3 Sample Size Determination

Assuming a cohort of 200 eligible patients is enrolled over a 2 year period, the follow-up period after the close of enrollment is 5 years, and the number of local recurrences follows a Poisson distribution, the upper bounds of 95 % confidence interval for the cumulative incidence of a local recurrence within 5 years would fall below 8 % if at most 8 local recurrences occurred as a first event among these 200 patients.

It was originally planned to have an additional 30 patients enrolled to account for patients who withdraw consent prior to surgery, are found to be ineligible after signing a consent form, convert to mastectomy, or are found to have a single contiguous area of malignancy at final pathology. During the course of the study, it was found that many patients were being deemed ineligible after enrollment because the distance between lesions was outside the allowable range. This caused a high rate of ineligibilities. The protocol was amended and the ineligibility rate has subsequently decreased. However, in order to obtain the 200 evaluable patients needed for the primary endpoint, the study will need to enroll a total of 265 (35 additional) patients. Hence the target accrual for the study is 265 patients.

16.4 Accrual Time

American Joint Committee on Cancer (AJCC) version 7.0 defines two macroscopic cancer foci in the same breast as multiple cancers if they are at least 0.5 centimeters apart. No distinction is made as to whether these are multifocal breast cancers (foci no more than 5 cm apart from each other in the same quadrant) or multicentric breast cancers (foci in different quadrants or foci in the same quadrant but more than 5 cm apart from each other). Moreover, the AJCC states that pathologic tumor size should be based only on the single largest tumor and recommends that pathologic T stage be designated as pTAny(m) where m indicated the number of multiple lesions. As the presence of multiple ipsilateral breast cancers (MIBC) are not routinely collected through AJCC staging or in the setting of breast cancer clinical trials, the incidence of this disease in general is not well known. Similarly, it is unknown how many women with MIBC have enrolled in clinical trials. Retrospective case studies estimate that 15 % of women diagnosed with breast cancer have MIBC. The estimated number of new female breast cancer cases in 2010 is 207,090 (Jemal *et al.*, 2010). Assuming that 15 % of these cases will have multiple ipsilateral breast cancers (31,064 cases) and 3 to 5 % of these multiple ipsilateral breast cancer cases will consider participating in a clinical trial, there will be 932 to 1553 potential candidates for this trial per year. The Alliance investigators accruing to currently open studies are interested and supportive of this trial design. For these reasons, accrual of 8 to 9 patients per month is anticipated to be feasible, for a total accrual time of about 25 months. The study requires an additional 5-6 months of accrual to meet the planned sample size.

16.5 Study Monitoring

16.51 Futility stopping rules

If more than 8 local recurrences are observed as a first event, the trial will stop as the 5 year local recurrence rate is unacceptably high.

A conversion to mastectomy rate of 25 % or more is considered to be unacceptably high. As such, consideration will be given to discontinuing

enrollment if 35 or more women among the first 100 women enrolled convert to mastectomy secondary to persistent positive margins or poor cosmesis within 6 months of BCS. The lower bound for 95 % binomial confidence interval for the conversion rate is 25.7 % (if 35 of 100 women convert to a mastectomy).

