12.2 Time of Registration: Pre-surgery vs Post-surgery

13.0 Treatment/Follow-up Decision at Evaluation of Patient

13.1 Follow-Up After Completion of WBI

Patients will be followed as per the test schedule for 5 years after completion of WBI.

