16.0 Statistical Considerations and Methodology**16.1 Overview**

A single arm phase II clinical trial design will be used to assess whether the local recurrence (LR) rate at 5 years in women with multiple ipsilateral breast cancers who undergo breast conserving surgery is greater than 8 %.

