16.6 Analysis Plan

16.61 Local Recurrence Rate

All eligible patients who have undergone surgery that was not converted to a mastectomy and who did not have a finding of single contiguous area of malignancy on final pathology will be included in the analysis of the primary endpoint.

The cumulative incidence of local recurrences will be estimated in the competing risk framework as described by Marubini and Valsecchi where regional recurrences, distant recurrences and death without a local recurrence will be considered competing risks and contralateral breast and non-breast second primary cancers will not be considered competing risk. A 95 % Poisson confidence interval for the cumulative incidence of a local recurrence within 5 years will be constructed.

Gentilini *et al.* reported that cumulative incidence of local recurrence differed in terms of estrogen receptor status, HER2/neu expression, Nottingham grade, and Ki-67 expression (univariately) (Gentilini *et al.*, 2009). Gray's test will be used to explore whether the cumulative incidence of local recurrence differs with respect to these factors as well as progesterone receptor status, number of positive lymph nodes, number of foci, t-stage, age, perception of quality of life as measured by LASA at registration (poor: 0 to 3; middling: 4 to 7; good/excellent: 8 to 10), and fatigue as measured by LASA at registration (none to little: 0 to 3; some: 4 to 7; a great deal: 8 to 10).

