16.62 Conversion to Mastectomy

The conversion rate to mastectomy secondary to persistent positive margins; poor cosmesis within the first year of attempting BCS; or inability to satisfy the radiation dose constraints on the boost to the lumpectomy bed of each site of disease

All eligible patients who have initiated surgery will be included in the analysis of conversion to mastectomy. A 95 % binomial confidence interval will be constructed for the percentage of patients who converted to mastectomy. Logistic regression analysis will be used to assess whether the likelihood of conversion to mastectomy differed with respect to patient and/or disease characteristics.

An interim efficacy analysis will not be performed; final analysis will be performed at year 7 after patients have at least 5 years of follow-up.

Patients enrolled subsequent to surgery will be excluded from this analysis.

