16.7 Data and Safety Monitoring

The principal investigator and the study statistician will review the study at least twice a year to identify accrual, adverse event and any endpoint problems that might be developing. The Alliance Data Safety Monitoring Board is responsible for reviewing safety data for this trial at least twice a year, based on reports provided by the Mayo Clinic Cancer Center Statistical Office.

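### Section 16.51 says the trial stops at the 9th local recurrence because the rate is unacceptably high, but its cut-off shows only that 8% can no longer be excluded, and the action is not named

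*Combined protocol and SAP*

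**What the plan says.** Section 16.1 sets the question, with the threshold in percent: whether "local recurrence (LR) rate at 5 years in women with multiple ipsilateral breast cancers who undergo breast conserving surgery is greater than 8". Section 16.3 assumes 200 eligible patients and a Poisson count, and states that the upper 95% bound "would fall below 8 % if at most 8 local recurrences occurred as a first event among these 200 patients".

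Section 16.51, headed as futility stopping rules, reuses that count and applies to any number exceeding "8 local recurrences are observed as a first event, the trial will stop as the 5 year local recurrence rate is unacceptably high". It gives no denominator, no time window and no statement of what stops.

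The next rule in 16.51 concerns conversion to mastectomy. It also speaks of an unacceptably high rate, there 25% or more. It supports its trigger of 35 in the first 100 women with a lower 95% binomial bound of 25.7%, and it names the action: "consideration will be given to discontinuing" enrollment.

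Elsewhere the plan puts no condition on the recurrence count:
- Section 13.1: "Patients will be followed as per the test schedule for 5 years after completion of WBI".
- Section 16.61: "A 95 % Poisson confidence interval for the cumulative incidence of a local recurrence within 5 years will be constructed".
- Section 16.62: no interim efficacy analysis, and the "final analysis will be performed at year 7 after patients have at least 5 years of follow-up".
- Section 16.7: "The Alliance Data Safety Monitoring Board is responsible for reviewing safety data for this trial at least twice a year".

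**The concern.** The rule attaches a conclusion to a count that does not support it. A limit chosen so that the upper bound stays below 8% tells us, once crossed, that 8% cannot be ruled out. To say that the rate is too high, the lower bound would have to be above 8%, which is how the neighboring mastectomy rule uses the same words.

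Two things are at stake. First, a trial that followed the text would declare breast conservation unacceptable in this population on data compatible with a rate well under 8%, and compatible with the 5.1% that section 1.1 cites as supportive. Second, whoever has to act on the rule is not told what to do. If the 9th event comes after accrual has closed, stopping enrollment has no effect, and the text does not say what else, if anything, is meant.

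**Working it through.** **Inputs.** 200 evaluable patients, a Poisson count and the 8% benchmark (16.1, 16.3). Trigger at 9 events (16.51). Accrual of 2 years (16.3), or about 25 months plus 5 to 6 more (16.4), so up to 31/12 = 2.58 years. The plan states no design rate; true rates of 4% and 5.1% are assumptions, the second being the published rate cited in 1.1.

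**1. Reproduce the plan's figure.** Exact two-sided 95% Poisson limits for k events in n patients: lower = χ²(0.025; 2k)/(2n), upper = χ²(0.975; 2k+2)/(2n).

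| Events / patients | Estimate | 95% limits |
|---|---|---|
| 8/200 | 4.0% | 1.73% to 7.88% |
| 9/200 | 4.5% | 2.06% to 8.54% |
| 24/200 | 12.0% | 7.69% to 17.86% |
| 25/200 | 12.5% | 8.09% to 18.45% |

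Eight is the largest count with an upper limit below 8%, as 16.3 says. The lower limit first passes 8% at 25. The sidedness is not stated in 16.3; a one-sided 95% upper limit would allow 9 events (7.85%), so the two-sided interval is the one that matches. The mastectomy figure also reproduces: the exact binomial lower limit for 35/100 is 25.73%.

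**2. The data at the moment of the trigger.** The 9/200 figure needs all 200 followed for 5 years, but the rule acts when events are observed. I simulated 200 patients with uniform accrual, constant hazard, events counted to 5 years, a clock from enrollment, and no dropout or competing risks (20,000 runs per setting). At a true 5.1%:
- The 9th event comes at a median of 4.7 years (2-year accrual) to 5.0 years (2.58-year accrual).
- It comes before accrual closes in about 0.2% of all runs or fewer. If accrual took 4 years, a duration not in the documents, this would be about 2.3%.
- About 725 patient-years have accrued. The hazard is 9/725 = 0.0124 per year, so the 5-year rate is 1 − exp(−5 × 0.0124) = 6.0%. The Poisson limits for 9 events are 4.115 and 17.085, which give 2.8% and 11.1%.
- The point estimate itself is above 8% in about 17% of stopped runs (about 9% at a true 4%).

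**3. When would nine events show a rate above 8%?** The lower limit passes 8% only if patient-years are below 5 × 4.115 / −ln(0.92) = 20.575 / 0.0834 = 247. That happens in about 0.1% to 0.2% of stopped runs at true rates of 4% to 5.1%.

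**4. Dependence on 200.** Section 16.3 enrolls 265 to obtain 200 evaluable, so the final number may differ. Upper limits: 8/197 = 8.002%, 8/198 = 7.961%, 9/213 = 8.021%, 9/214 = 7.984%. Eight events fail the criterion at 197 or fewer, and nine meet it at 214 or more.

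**The case against.** The strongest reply is that the rule sits under a futility heading and is right as a futility rule: with 200 evaluable patients a 9th event puts the 16.3 criterion out of reach, and the reason clause may be loose shorthand for a rate that cannot be shown to be acceptable. The first half stands, and the trigger should be kept. The second half is weaker, because the next rule in the same section rests the same words on a lower limit.

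A reader might infer that 16.51 creates a large risk of a false stop: the Poisson probability of more than 8 events in 200 is 41% at a true 4% and 69% at 5.1%. Those probabilities belong to the sample size and the criterion in 16.3. A trial with 9 events in 200 misses that criterion with or without 16.51, and rewording the rule does not change them.

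A reader might also infer that stopping ends follow-up and truncates the primary estimate. No section says so. Sections 13.1, 16.61 and 16.62 set follow-up, the 5-year estimate and the final analysis without reference to the count. Equally, none says that they continue after this stop. That is an ambiguity to close, not a demonstrated loss of data.

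It is also fair to say that 9/200 = 4.5% is the mildest picture. At the trigger the estimate is typically higher, though 8% still lies inside the interval in all but about 0.1% to 0.2% of stopped runs.

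**Conclusion.** The point holds in this form. The trigger is a coherent futility rule, the stated reason for it is not supported by the plan's own figures, and the action is undefined. A 9th event means that an upper 95% limit below 8% is out of reach at 200 evaluable patients. It does not show that the rate exceeds 8%, which with 200 fully followed patients would take 25 events.

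The interval results for fixed counts are exact and rest only on the two-sided Poisson interval that reproduces 16.3. The timing and the estimate at the trigger are approximate: they assume a true rate, constant hazard and an enrollment clock, whereas 13.1 counts follow-up from the end of radiation. The conclusion that the 9th event almost always falls after enrollment closes is stable across the accrual times that the documents give.

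This should be corrected because the rule governs the primary endpoint and states a safety conclusion. It is a defect of wording and of a missing instruction, and no planned calculation changes.

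**What to change.** In 16.51 replace the sentence on local recurrence with:

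> If more than 8 first-event local recurrences within 5 years are observed in the primary analysis set, the futility rule is met because, with the planned 200 evaluable patients, the upper 95% limit can no longer fall below 8%; this does not by itself show that the rate exceeds 8%. Any enrollment still open stops and the DSMB reviews the data; enrolled patients complete the follow-up in 13.1, and the 5-year cumulative incidence with its 95% CI (16.61) is reported whatever the count.

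State separately, for the final analysis only, that the criterion is an upper 95% limit below 8% at the actual evaluable number. Keeping this apart from the monitoring rule matters because the final evaluable number is unknown while enrollment is open, and a fixed count and a floating one in the same rule would conflict.

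**Cost.** Text only: no patients or visits beyond those already planned, and an early cluster of recurrences still stops open enrollment. Follow-up would continue in a trial that may already have missed its criterion, and the DSMB may need a review outside its twice-yearly schedule.

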3.14 Foci of Breast Cancer

Upon clinical exam and pre-operative imaging by mammogram +/- MRI, two or three foci of biopsy proven breast cancer separated by ≥ 2 cm of normal breast tissue.

Foci must include *at least one focus of invasive breast carcinoma with another focus of either invasive breast carcinoma or ductal carcinoma in situ (DCIS)*.

No more than 2 quadrants with biopsy proven breast cancer.

Note: The shortest distance between lesions must be reported on mammogram +/- MRI and eligibility criteria must be met on both, if both are obtained.

Note: Patient is eligible for study if lesion is not visualized on all imaging modalities (i.e., any of the lesion(s) is/are visualized on MRI but not on mammogram OR visualized on mammogram but not on MRI). Ultrasound cannot be used to determine patient eligibility; eligibility to be determined by bilateral mammogram +/- MRI **only**. Fine needle aspirate of the second or third lesion to document malignancy is allowed if the first focus is shown to be invasive by core needle biopsy. Patient may remain on study if, upon pathological assessment, two or three lesions identified on pre-operative imaging represent one contiguous lesion.

3.15 Patients may be registered AFTER surgery and PRIOR TO radiation therapy if either of the criteria is met:

1. An area of atypia > 2 cm from the index lesion excised at the time of cancer operation is upgraded to DCIS or invasive carcinoma thereby identifying MIBC.

OR

2. Patient underwent resection of two or three foci of malignancy by breast conservation surgery with a minimum of one invasive focus of breast cancer and a minimum of 2 cm of normal breast tissue between the lesions on final pathology.

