3.28 Systemic Illnesses or Concurrent Disease

Co-morbid systemic illnesses or other severe concurrent disease which, in the judgment of the investigator, would interfere significantly with whole breast irradiation (such as connective tissue disorders, lupus, scleroderma).

3.29a Uncontrolled Intercurrent Illness

Uncontrolled intercurrent illness including, but not limited to, ongoing or active infection, symptomatic congestive heart failure, unstable angina pectoris, cardiac arrhythmia, or psychiatric illness/social situations that would limit compliance with study requirements.

3.29b Bilateral Breast Cancer

Prior or current LCIS, DCIS or invasive breast cancer in the opposite breast (i.e., bilateral disease is not allowed).

3.29c Disallowed Prior Treatments

Treatment including radiation therapy, chemotherapy, biotherapy, hormonal therapy for this cancer prior to surgery (i.e., any neoadjuvant chemotherapy or endocrine therapy is not allowed). Patients who undergo surgical resection with breast conservation and then are treated with adjuvant systemic therapy are eligible to enroll prior to the start of radiotherapy.

3.29d Partial Breast Radiation

Planned partial breast radiation.

3.29e Known BRCA Mutations

Patients with known BRCA mutations. Patients who are not tested or whose testing result is not returned at the time of registration are not excluded from registering to this study.

3.29f Other Active Malignancies

Other active malignancy \leq 5 years prior to registration.

Exceptions: Non-melanotic skin cancer or carcinoma-in-situ of the cervix.

Note: If there is a history of prior malignancy, they must not be receiving other specific treatment for their cancer.

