13.6 Definition of Cancel

A patient is deemed a *cancel* if she withdrew consent prior to surgery. On-study material and the End of Active Treatment/Cancel Notification Form must be submitted. No further data submission is necessary.

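### The plan conflicts on whether mastectomies for an unmet radiation dose constraint reach the final conversion rate; a lesser point is that the interim trigger is read in a wider population than that rate

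*Combined protocol and SAP*

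**What the plan says.** **Endpoint.** Section 16.62 counts conversions for persistent positive margins, and for "poor cosmesis within the first year of attempting BCS; or inability to satisfy the radiation dose constraints" on the boost. Sections 2.21 and 16.2 list the same three reasons. On the population, 16.62 says "All eligible patients who have initiated surgery will be included in the analysis of conversion to mastectomy", and then "Patients enrolled subsequent to surgery will be excluded from this analysis".

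**Women whose dose constraint is not met.** Sections 7.622 and 7.634 take them off protocol therapy, recommend mastectomy and point to 13.2. Section 13.2 has two paragraphs that can both apply:
- The first sends women who convert for whatever reason in the year after initial surgery to observation, with data submitted up to the mastectomy.
- The second terminates participation in two situations: persistent positive margins in women who decline mastectomy, and an unmet dose constraint. It lists the on-study, surgery, pathology and end-of-treatment forms and asks for nothing afterwards.

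**Eligibility.** Sections 7.6, 7.617 and 13.3 label women who cannot or do not get a boost as ineligible. Section 13.5 defines ineligibility by whether the criteria were met at registration.

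**Interim trigger.** Section 16.51 states: "A conversion to mastectomy rate of 25 % or more is considered to be unacceptably high". It considers ending enrolment when "35 or more women among the first 100 women enrolled convert to mastectomy secondary to persistent positive margins or poor cosmesis within 6 months", counted from surgery, and gives 25.7% as the lower 95% limit for 35 of 100. Enrolled women can include those registered after surgery (3.15: "Patients may be registered AFTER surgery and PRIOR TO radiation therapy if either of the criteria is met"; 3.29c: "Patients who undergo surgical resection with breast conservation and then are treated with adjuvant systemic therapy are eligible to enroll") and cancels, which 13.6 defines as a patient "if she withdrew consent prior to surgery".

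**The concern.** **Final estimate (main point).** The order of events matters. The constraint fails first; mastectomy is then recommended and, if accepted, happens later. A site that applies the second paragraph of 13.2 when the constraint fails may close the record before the mastectomy. Separately, an analyst who takes the ineligible label in 7.6 at face value would drop the woman from 16.62. Each route removes conversions of one named type, so the published rate would be expected to understate how often breast conservation fails in this population.

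**Trigger (minor point).** The 35 of 100 and its 25.7% limit describe the 16.62 rate only if all 100 women belong to the 16.62 population. Cancels before surgery cannot convert. Post-surgery registrants are expected to convert less, because they had not converted by registration. Both groups make the trigger harder to reach. Women later found ineligible, whom 16.3 describes as numerous before an amendment, have no predictable direction.

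**Working it through.** **1. Side-by-side reading for a woman whose constraint fails and who then has a mastectomy**

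| Text applied | Consequence for the 16.62 rate |
|---|---|
| 13.2, first paragraph (if within a year) | mastectomy recorded; counted |
| 13.2, second paragraph | submission ends when the constraint fails; a later mastectomy may go unrecorded |
| 7.6, 7.617, 13.3 label | ineligible; outside 16.62 |
| 13.5 definition | eligible if the criteria were met at registration; inside 16.62 |

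In the second paragraph of 13.2, the margin item is limited to women who decline mastectomy. The dose-constraint item has no such limit, so the text does not settle which paragraph governs.

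**2. Size of the loss.** The documents do not say how many conversions are of this type. Let d be their share of the analysis population, assumed to be 1, 2 or 5 percentage points. Take a true rate of 25%, the level that 16.51 calls too high.
- Women kept but conversions not recorded: estimate = 0.25 − d = 24, 23 or 20%.
- Women excluded, all of whom had converted: estimate = (0.25 − d)/(1 − d) = 0.24/0.99, 0.23/0.98, 0.20/0.95 = 24.2, 23.5 or 21.1%.
- More generally, if a share e of women is excluded and a fraction c of them had converted, the estimate is (0.25 − c·e)/(1 − e). This is below 25% whenever c exceeds 0.25.

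**3. The plan's own trigger figure.** The exact (Clopper-Pearson) 95% lower limit for 35/100 is the 2.5% point of Beta(35, 66) = 25.7%, as stated. For 34/100 it is 24.8%, so 35 is the smallest count out of 100 with a lower limit above 25%. The arithmetic is sound.

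**4. Trigger when some of the 100 are outside 16.62.** Let o be the number outside, q their conversion rate and p the true rate inside. P(trigger) = P(X + Y ≥ 35), with X ~ Bin(100 − o, p) and Y ~ Bin(o, q). Both o and q are assumed; the documents give neither.

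| o | q | p = 35% | p = 40% |
|---|---|---|---|
| 0 | – | 53.8% | 87.0% |
| 10 | 0 | 25.2% | 62.4% |
| 20 | 0 | 6.5% | 28.3% |
| 20 | 5% | 10.5% | 36.6% |
| 20 | 10% | 15.7% | 45.3% |

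**5. Counts that keep the plan's criterion on fewer women.** The smallest counts with an exact lower limit above 25% are 32/90 (25.7%), 29/80 (25.8%) and 26/70 (25.9%). With 80 qualifying women, 29 or more is reached with probability 44.9% at p = 35% and 78.7% at p = 40%. Keeping 35 gives 6.5% and 28.3%.

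**6. Scope of the look.** Section 16.51 counts two reasons within 6 months; 16.62 has three and allows a year for cosmesis. Adjuvant therapy may start up to 12 weeks after surgery (7.5), and the constraint may be judged up to 8 weeks after chemotherapy (7.622). So 12 + 8 = 20 of 26 weeks can pass before the chemotherapy itself is counted. Leaving dose-constraint conversions out of a 6-month look is therefore understandable, but 16.51 does not say what is left out.

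**The case against.** **On the final estimate.** The natural reading of 13.2 is that a woman who has the mastectomy falls under its first paragraph, which covers every reason. Even the second paragraph requires surgery, pathology and end-of-treatment forms, and their fields cannot be seen. Excluding these women as ineligible would defeat a component that the plan names three times, and 13.5 already ties ineligibility to registration. All of this stands. It shows that the intended answer is probably to count them. It does not remove the conflict, because a mastectomy after termination can still be missed and nothing in 16.62 overrides the label in 7.6. A reader might infer that these conversions are certainly lost; the documents show only that they can be.

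A reader might also judge the damage by whether the final interval falls wholly below 25%. Section 16.62 sets no threshold; 25% appears only in 16.51. The shift in the estimate is therefore the right measure.

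**On the trigger.** It is advisory, a monitoring look may be simpler than the final analysis, and 16.7 adds a review at least twice a year. The account in 16.3 of raising accrual to 265 suggests that the first 100 are already enrolled. These objections stand and keep the point minor. Three stronger inferences fail:
- That 25.7% is wrong: it reproduces.
- That post-surgery registrants dilute the final rate: 16.62 excludes them.
- That the look is a strict lower bound on the final rate: the first 100 are a sample, and eligibility changed during the study, so their rate need not lie below the final one.

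**Conclusion.** The point holds as a minor one, with the weight on the final estimate. The two paragraphs of 13.2, and the two meanings of ineligible in 7.6/7.617/13.3 and 13.5, leave it open whether a named component of the conversion endpoint is recorded and analysed. If it is lost, the expected direction is downward: 1 to 5 percentage points at a true 25% if unrecorded, and about 0.8 to 3.9 points (25 − 24.2 to 25 − 21.1) if excluded. This rests on an assumed share of 1 to 5 points and, for exclusion, on all the excluded women having converted.

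The trigger mismatch is real but secondary. Its effect depends on the make-up of the first 100, which is not in the documents; it is nil if all 100 qualify. It matters only while enrolment can still be affected.

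**What to change.** 1. **13.2:** reconcile the two paragraphs so that mastectomy (yes/no, date, reason) is recorded for every woman whose dose constraint was not met. The recording period should be no shorter than the one 16.62 uses for this reason. The one-year limit in 16.62 is attached to cosmesis and none is given for the dose constraint, so a one-year cut-off could itself miss events.
2. **16.62:** state that eligible means eligible at registration, as in 13.5, so that women labelled ineligible for lack of a boost stay in this analysis.
3. **16.51, only if enrolment can still be affected:** define the denominator as the first 100 eligible women registered before surgery who have started breast-conserving surgery; 35/100 and 25.7% then stand. If the look must use the first 100 enrolled, apply the count that matches the number who qualify, for example 32/90, 29/80 or 26/70. Add that the look omits dose-constraint and later cosmesis conversions and is therefore expected to understate the 16.62 rate.

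The cost is wording in three sections and one short data item for a few patients. Items 1 and 2 remain useful after accrual closes, because 16.62 places the final analysis at year 7. No dose, constraint or treatment rule is altered.
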